11.1 Power Analyses

As this study is designed as a proof of concept study to determine whether the ViaNAsE device is able to deliver insulin to the CNS as evidenced by increased CSF insulin levels following insulin administration relative to saline placebo, power calculations have not been conducted. However, the proposed sample size is larger than two previous studies (Born et al. 2002; Fishel et al. that showed that administering insulin increased CSF insulin levels.

12.0 POTENTIAL RISKS

12.1 Safety of Intranasal Insulin

Safety issues pertaining to INI administration for the treatment of diabetes have been extensively explored for over two decades (Pontiroli, Alberetto et al. 1982). For diabetes treatment, absorption enhancers must be used to increase the transport of insulin across the nasal membrane to the periphery due to the fact that peripheral bioavailability of insulin without absorption enhancers is less than 1% (Illum 2002). A recent safety study of INI administration without absorption enhancers demonstrated no treatment induced changes in blood glucose levels, nasal airway patency, or transnasal pressure gradient (Kupila, Sipila et al. 2003). There are no known serious risks associated with INI without enhancers. A recent industry report raised the issue of rare but significant increases in lung cancer in smokers treated with inhaled insulin; six of 4740 patients taking inhaled insulin developed lung cancer compared with one of 4292 patients who received an active comparator (incidence per 100 patient years exposure, 0.13 vs 0.02). However, the inhaled insulin protocol used for diabetes treatment in this report included absorption enhancers to maximize delivery to lungs, whereas the nose-to-brain delivery device to be used in this study greatly minimizes lung delivery.

Regarding the risk of hypoglycemia, at least five peer reviewed human studies (Kern, Born et al. 1999, Born, Lange et al. 2002, Kupila, Sipila et al. 2003, Benedict, Hallschmid et al. 2004, Stockhorst, de Fries et al. Submitted for publication) and four preliminary studies (Reger, Watson et al. 2006, Reger, Watson et al. 2008, Reger, Watson et al. 2008) (Craft, Baker et al. 2012) revealed no change in blood glucose levels following intranasal insulin administration with doses that included 40 International Units 4 times daily for two months. There was one exception with the case of a single participant who experienced mild hypoglycemia (52 mg/dl) after skipping a meal and engaging in sustained vigorous exercise. In

addition, a recent safety study (Kupila, Sipila et al. 2003) examined intranasal insulin administration of 60 International Units once a day for three weeks in 21 healthy adults. This randomized, double-blind, placebo-controlled crossover trial measured blood glucose levels six times a day during the first two and the last two days of treatment. Pre- and post-treatment blood laboratory tests and nasal examinations were performed. The nasal studies included rhinoscopy to detect local irritation, a saccharin particle test to analyze mucociliary clearance, and rhinomanometry to evaluate nasal airway patency and transnasal pressure gradient. Results indicated no change in blood glucose values with insulin, and no change in the frequency of glucose values above 3.0 mmol/L. The only symptomatic hypoglycemic value occurred during placebo treatment. Insulin treatment had no effect on other laboratory values (C-peptide, total cholesterol, HDL, LDL, triglycerides, creatinine, glutamyl transferase), blood pressure, or body weight. In addition, nasal examinations revealed no adverse effects or functional disturbances following intranasal insulin administration. No serious adverse effects of treatment were observed in the preliminary studies (Reger, Watson et al. 2006, Reger, Watson et al. 2008, Reger, Watson et al. 2008, Craft, Baker et al. 2012).

12.2 Risks associated with use of the ViaNase® device

Because the use of the device will be supervised directly by the study nurse the risks of adverse events is extremely low. Participants could experience some discomfort to their eyes or face if they do not hold the device to their nose as directed; however, again, the study nurse will carefully instruct and oversee device use so that any errors can be immediately corrected.

12.3 Lumbar Puncture

Lumbar puncture may be associated with pain during the performance of the procedure. This is usually temporary and confined to the lower back. Headache may occur in about 5% of elderly people who undergo lumbar puncture. Less commonly, in about 1-4% of participants, a persistent low-pressure headache may develop, probably due to leakage of CSF. Lower rates of post-LP headache have been noted in elderly patients, and when atraumatic (Sprotte) needles are used. If a post-LP headache persists it may need additional treatment, e.g. with fluids and analgesics. Uncommonly a blood patch (injection of some of the participant's blood to patch the CSF leak) may be needed. Potential but rare risks of lumbar puncture include infection, damage to nerves in the back, and bleeding into the CSF space. The risk of these is much less than 1%.

12.4 Blood Draw

The risks of blood draw include pain from the needle, bruising or infection at the site of venipuncture, or fainting as a response to blood draw. Approximately 50mls of blood will be drawn for routine and biomarker laboratory assessments over the course of this study.

14.0 STUDY DRUG

All participants will take receive one dose of INI (20 International Units) or placebo, administered approximately 30 minutes prior to the LP.

14.1 Humulin® R U-100 Insulin

Humulin® R U-100 (NDC: 0002-8215, Eli Lilly & Company) is a polypeptide hormone structurally identical to human insulin synthesized through rDNA technology in a special non-disease-producing laboratory strain of *Escherichia coli* bacteria. Humulin R U-100 has the empirical formula C₂₅₇H₃₈₃N₆₅O₇₇S₆ and a molecular weight of 5808 Da. Humulin R U-100 is a sterile, clear, aqueous, and colorless solution that contains human insulin (rDNA origin) 100 units/mL, glycerin 16 mg/mL and metacresol 2.5 mg/mL, endogenous zinc (approximately 0.015 mg/100 units) and water for injection. The pH is 7.0 to 7.8. Sodium hydroxide and/or hydrochloric acid may be added during manufacture to adjust the pH.

More information about the Humulin® R U-100 insulin, including risks, contraindication and adverse reactions can be found in the the US package insert (USPI).

14.2 Placebo (Sterile Saline)

The placebo will consist of sterile saline.

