SECONDARY OBJECTIVES	
 1. To test the hypothesis that memory performance measured with a list learning test (Auditory Verbal Learning Test) will be enhanced after insulin administration relative to placebo 2. To test the hypothesis that the CSF Aβ42/40 and the CSF Aβ/tau ratios will increase after insulin administration relative to placebo
PRIMARY OUTCOME MEASURE	CSF insulin
SECONDARY OUTCOME MEASURES	Memory test, CSF insulin, A β 40, A β 42, total tau, and phospho-tau 181
STUDY DESIGN	Single-site, double-blind, placebo-controlled study
SAMPLE SIZE	
 • n=30
SUMMARY OF KEY ELIGIBILITY CRITERIA	
 • Cognitively normal or • Diagnosis of aMCI (Petersen criteria) • Age: 55 to 85 yrs (inclusive)
DRUG DOSAGE & FORMULATION	20 International Units Humulin [®] R U-100 or matching placebo (saline)
DURATION OF PARTICIPATION	The approximate timeline for this 21 month study is projected as: 1) approximately 1 months for study startup activities including IND submission and IRB approval, and training; 2) approximately 18 months for data collection; 3) 2 months for assay and data analysis
PLACEBO	A matching placebo (sterile saline) will be used
ROUTE OF ADMINISTRATION	Intranasal
PROCEDURES	Physical and neurological exam, nasal examination, lumbar puncture, Vitals, Clinical Labs, CSF and blood analysis & banking and genotyping.

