Methods: Twenty-six sites enrolled 289 participants with MCI or mild AD in this randomized, double-blind, Phase II/III trial (NCT01767909). Adults 55 to 85 years of age with diagnoses of amnestic MCI or AD (National Institute on Aging-Alzheimer's Association criteria) with Mini-Mental State Exam (MMSE) scores >19, Clinical Dementia Ratings (CDR) of 0.5 or 1, and delayed Logical Memory scores within a specified education-adjusted range were eligible. Participants with diabetes requiring medication were excluded, as were participants who had used insulin within one year of the screening

visit. Participants were randomized on a 1:1 basis using a covariate-adaptive algorithm that weighted MMSE, apolipoprotein E-ε4 (APOE-ε4) allele carriage, study site, sex, and age based on previous work indicating these factors may impact treatment response. Participants received 40 International Units of insulin or insulin diluent placebo (Humulin R U-100 or insulin diluent, Eli Lilly, Indianapolis, USA) daily for 12 months. At the end of the 12-month blinded phase, all participants were offered open-label insulin treatment for 6 months. The primary outcome (Alzheimer's Disease Assessment Scale for Cognition-12/ADAS-Cog12) was administered at baseline and then at 3 month intervals. Secondary functional outcomes (Alzheimer's Disease Cooperative Study-Activities of Daily Living Scale for MCI; CDR Sum of Boxes) were assessed at 6 month intervals, as was a memory composite (Free and Cued Selective Reminding Test and Story Recall). Cerebrospinal fluid biomarkers (Aβ42 and Aβ42/tau ratio) and magnetic resonance imaging hippocampal and entorhinal cortex volumes were measured at baseline and after 12 months.

Device issues. Intranasal delivery device monitoring revealed no safety issues. However, for the first 49 participants, the delivery device had frequent malfunctions (i.e. failure to turn on) that impacted dosing reliability. At that time, a newly available device was introduced (Precision Olfactory Device/POD, Impel NeuroPharma, Seattle, USA) which was used by the remaining 240 participants with good reliability.

Results: Demographic characteristics of enrolled participants are presented in Table 1. Retention was excellent, with only 25 participants discontinuing treatment during the blinded phase, and 15 also discontinuing study visits during the blinded phase. Quarterly DSMB reviews did not detect any safety issues and approved unmodified continuation of the trial.

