5.0 STUDY OVERVIEW

The study will consist of a single site, randomized, double-blind trial comparing the acute effects of INI (20 International Units) or placebo delivered with the ViaNase device on CSF insulin levels, AD biomarkers and memory. At study entry, participants will be randomized to receive either an acute dose of insulin or of placebo first, and the other substance on a second visit. Participants who are cognitively normal or who have aMCI (n=30) will be enrolled. The primary outcome measure will consist of CSF insulin levels. Secondary measures will include a memory test and CSF biomarker levels.

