7.2 Baseline (Visit 2)

Results from all screening procedures must be reviewed and all inclusion/exclusion criteria must be met prior to proceeding to baseline. For participants whose screening visit was waived because they had received ADRC evaluations within the past 12-months will sign an informed consent form and HIPAA Authorization prior to administration of any study-related procedures.

According to the randomization schedule, the participant will receive a dose of 20 International Units insulin or placebo administered with the ViaNase device. They will then begin preparations for the lumbar puncture. After preparation, the immediate recall section of the AVLT will be administered. Blood for plasma biomarkers will then be collected immediately before and after participants undergo the lumbar puncture. Fasting plasma insulin, glucose, A β 40 and A β 42 will be measured. Additional plasma and serum will be collected and banked.

Lumbar puncture will then be performed in the morning after a minimum 8-hour overnight fast. CSF samples will be used to measure levels of insulin, A β 42, A β 40, total tau, and phospho-tau181. Additionally, CSF sample will be banked for future exploratory analysis. CSF will be collected and immediately frozen upright on dry ice. Site staff will call the participant within 24 hours from the lumbar puncture procedure to inquire about the participant's well-being and possible adverse events. Following the lumbar puncture, the delayed recall section of the AVLT will be administered. Participants will then receive a snack and instructions about post-lumbar puncture care.

7.3 Visit 3

Visit 3 will be scheduled within 2 to 6 weeks following Visit 1. Vital signs and weight will be obtained, a nasal examination will be conducted, adverse events and concurrent medications will be recorded. Procedures will follow the schedule outlined for Visit 1, except that the alternate compound (either saline or 20 International Units insulin) will be administered.

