14.6 Intranasal Administration

Insulin or placebo will be administered with a ViaNase™ drug delivery device (Kurve Technology, Bothell, WA). ViaNase™ specifically targets olfactory delivery to maximize drug transport to the CNS. This device releases a metered insulin dose into a chamber covering the participant's nose. The insulin or placebo is then inhaled by breathing evenly over a specified period. This method allows administration of smaller particle sizes to increase deposition in the upper nasal cavity while minimizing transport to the lungs. A volume of about 0.7 mL of insulin or placebo will be administered each time.

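### The placebo called matching is saline without the active product's excipients, so the memory and nasal adverse-event contrasts are insulin plus vehicle against saline, and sensory blinding is unverified

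*Combined protocol and SAP*

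**What the plan says.** The synopsis says "A matching placebo (sterile saline) will be used". Section 14.2 gives the whole composition: "The placebo will consist of sterile saline". Section 14.1 describes the active product, Humulin R U-100, as containing "glycerin 16 mg/mL and metacresol 2.5 mg/mL" as well as zinc. It adds that "Humulin R U-100 is a sterile, clear, aqueous, and colorless solution".

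The study is a two-period crossover. By Section 5.0, "participants will be randomized to receive either an acute dose of insulin or of placebo first, and the other substance on a second visit". On delivery, Section 14.6 says "The insulin or placebo is then inhaled by breathing evenly over a specified period". Section 14.4 states that participants and site staff are blinded, with an exception for the nurse who prepares the product. No section describes masking of smell, taste or nasal sensation, or any check of the blind.

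Section 4.0 reports that Preliminary Study 2, with the same insulin product, gave "40 International Units of insulin or insulin diluent placebo". The protocol gives no reason for using saline here.

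**The concern.** A placebo should differ from the active treatment only in the active ingredient. Here it also differs in the vehicle. Two consequences follow, and they should be kept apart.

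1. **Confounding with vehicle.** If metacresol or glycerin irritates the nose, or if the vehicle has any other short-term effect, the treatment contrast contains that effect and no analysis of these data can separate it. This does not depend on anyone guessing.
2. **Possible unblinding.** The same person inhales both products, so a perceptible difference could be noticed. The AVLT is given after dosing at both visits and depends on effort and expectation. Section 4.2 intends the secondary measures as support for access to, and efficacy in, the CNS, so a memory difference would be read as a drug effect.

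Nasal adverse events are exposed to both. Section 11.0 plans no treatment comparison of adverse events, but Section 19.4 allows the DSMB to recommend stopping if it sees a convincing one. CSF insulin is an assay value that expectation cannot move, and nothing in the documents suggests that the vehicle would change it.

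**Working it through.** The plan has no figure to reproduce on this point: Section 11.1 says that power was not calculated, and no alpha or sidedness is stated.

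**Step 1. Composition of the two products**

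| Component | Active (14.1) | Placebo (14.2) |
|---|---|---|
| Insulin | 100 units/mL | none |
| Metacresol | 2.5 mg/mL | none listed |
| Glycerin | 16 mg/mL | none listed |

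**Step 2. Excipient load per administration.** Section 14.0 gives 20 IU, Section 14.1 gives 100 units/mL, and Section 14.6 gives a volume of about 0.7 mL.

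- 20 IU / 100 units/mL = 0.2 mL. Metacresol: 0.2 × 2.5 = 0.5 mg. Glycerin: 0.2 × 16 = 3.2 mg.
- If that 0.2 mL is made up to 0.7 mL: metacresol 0.5 / 0.7 = 0.71 mg/mL; glycerin 3.2 / 0.7 = 4.6 mg/mL, assuming that the added volume contains neither.
- If 0.7 mL is undiluted product: metacresol 0.7 × 2.5 = 1.75 mg; glycerin 0.7 × 16 = 11.2 mg. The content would then be 0.7 × 100 = 70 units, which does not agree with 20 IU.

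The three statements do not fit together unless something is added, and the documents do not say what. The concentration that participants meet is therefore unknown. The products differ under each reading.

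**Step 3. What the earlier saline-controlled study shows.** Preliminary Study 1 (Sections 3.2 and 3.8) compared saline with another brand of regular insulin. Persons affected are the Table 3 percentage times the group size (30 placebo, 36 low dose, 38 high dose).

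- Rhinitis: 1, 6 and 3 persons. Low dose against placebo, Fisher p = 0.12; pooled insulin 9/74 against 1/30, p = 0.27.
- Nose bleed: 0, 3 and 1 persons. Pooled 4/74 against 0/30, p = 0.32.
- Mean total adverse events, as reported: 1.44 on low dose against 0.80 on placebo, p = 0.04.

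The direction is compatible with a nasal effect of the active product. It is not conclusive, and insulin cannot be separated from vehicle.

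**Step 4. Illustration for the AVLT.** Assume no true effect, 30 complete pairs, a two-sided 5% paired t-test, and an average expectation shift of d SDs of the paired difference. The false-positive rate is P(|T| > t(0.975; 29)), where T is noncentral t with 29 degrees of freedom and noncentrality d × √30.

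| d | d × √30 | False-positive rate |
|---|---|---|
| 0.05 | 0.27 | 5.8% |
| 0.1 | 0.55 | 8.3% |
| 0.2 | 1.10 | 18.5% |
| 0.3 | 1.64 | 35.5% |

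Here d is an average over all 30 participants. If a net quarter identified the treatment order and each shifted by 0.2 SD, then d = 0.25 × 0.2 = 0.05. If half did, d = 0.5 × 0.2 = 0.1. None of these shifts comes from the documents.

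**The case against.** A reader might infer that the blind is weak or broken because each participant can compare the two products. The documents do not support that, for four reasons.

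- No section says that the excipients can be smelled, tasted or felt. The insulin is clear and colourless and Section 14.6 gives one volume for both products, so matching may have been meant as appearance and volume.
- Noticing a difference does not reveal which product is insulin, and at the first dosing visit there is nothing to compare with.
- If the insulin is diluted, the excipient concentrations fall to less than a third of the vial strength (0.71 against 2.5 mg/mL for metacresol).
- A gap between doses makes sensory comparison harder. The gap itself is not fixed by the text: Section 7.3 says "Visit 3 will be scheduled within 2 to 6 weeks following Visit 1", and Visit 1 is Screening in Section 7.1 and Table 4.

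Nasal events are not only self-reported, since a nasal examination is done at each visit (Section 9.1, Table 4). Saline also has a precedent: Preliminary Study 1 used it with the ViaNase device, including an arm at 20 IU per administration. Finally, the documents do not give the composition of insulin diluent, so its suitability as a vehicle control is not established by them.

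All of this stands, and it limits the claim about blinding to unverified. It does not touch the vehicle confound, which follows from composition alone. Visual similarity does not address smell or nasal sensation, and a precedent for saline does not make saline a matched vehicle.

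**Conclusion.** The point holds in a limited form. Saline is not matched to the active product in composition, so the AVLT and nasal adverse-event contrasts estimate insulin plus vehicle against saline. Blinding by smell, taste or nasal sensation is neither secured nor checked; it has not been shown to fail.

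The size of any bias is unknown. The rates of about 6% to 36% are conditional on assumed shifts of 0.05 to 0.3 SD, 30 complete pairs and a two-sided 5% test, and should not be read as estimates for this trial. The primary CSF insulin comparison is largely untouched. This is an inexpensive improvement to a secondary aim and to the safety reading, not a threat to the main result.

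**What to change.** **Preferred.** Use insulin diluent as the placebo, as in Preliminary Study 2, after confirming that its excipients match those of the active product as administered. Amend the synopsis, Section 14.2 and Section 14.4 to say so.

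**If diluent cannot be obtained.** Delete the word matching and give the reason for saline. Record a treatment guess from the participant and from the AVLT tester at each dosing visit, after delayed recall. Asking before recall could itself prime expectation. Report AVLT and nasal adverse events as a contrast in which vehicle was not controlled and blinding was not verified.

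**In either case.** Reconcile Sections 14.0, 14.1 and 14.6 on dose, strength and volume, and state what any added volume contains. Without that, a match between placebo and active product cannot be confirmed.

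**Cost.** The preferred change needs a protocol and IND amendment, procurement of diluent, and acceptance of a different placebo from Preliminary Study 1. The fallback needs wording changes and one extra form item per visit.

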14.3 Randomization

Eligible participants will be randomized on a 1:1 schedule to receive either insulin or saline first.

14.4 Blinding

Neither participants or site personnel will know whether insulin or saline is being administered. Exceptions will be the study nurse who is directly involved in preparing the insulin or placebo, as well as preparing DSMB reports.

14.5 Study Drug Dispensing

Study drug will be inserted into the chamber of the ViaNase™ by the study nurse.

14.6 Intranasal Administration

Insulin or placebo will be administered with a ViaNase™ drug delivery device (Kurve Technology, Bothell, WA). ViaNase™ specifically targets olfactory delivery to maximize drug transport to the CNS. This device releases a metered insulin dose into a chamber covering the participant's nose. The insulin or placebo is then inhaled by breathing evenly over a specified period. This method allows administration of smaller particle sizes to increase deposition in the upper nasal cavity while minimizing transport to the lungs. A volume of about 0.7 mL of insulin or placebo will be administered each time.

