1.1 Primary Aim

To test the hypothesis that CSF insulin levels will increase 30 minutes after receiving a 20 International Units dose of insulin delivered with the ViaNase or device, compared to levels achieved 30 minutes after placebo

1.1.1 Secondary Aim 1

1. To test the hypothesis that memory performance measured with a list learning test (Auditory Verbal Learning Test) will be enhanced after insulin administration relative to placebo

1.1.2 Secondary Aim 2

1. To test the hypothesis that the CSF A β 42/40 and the CSF A β 42/tau ratios will increase after insulin administration relative to placebo

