4.1 Rationale for Dosage Selection

The dosage selected (20 International Units INI) has been used in two prior studies with positive results as described above.

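### The 0.7 mL administration volume in section 14.6 does not match the 20 IU dose: at the only stated strength (U-100) it is 70 IU, and nothing in the text reconciles the two.

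*Combined protocol and SAP*

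**What the plan says.** The dose is consistent across the combined protocol and SAP:

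- The synopsis ties dose to product in one line: "20 International Units Humulin [®] R U-100 or matching placebo (saline".
- The primary aim (1.1) concerns a "20 International Units dose of insulin delivered with the ViaNase or device".
- The study overview (5.0) describes a trial "comparing the acute effects of INI (20 International Units) or placebo delivered with the ViaNase device on CSF insulin levels".
- The dose rationale (4.1) rests on prior use: "The dosage selected (20 International Units INI) has been used in two prior studies".
- The visit description (7.2) says "the participant will receive a dose of 20 International Units insulin or placebo administered with the ViaNase device", and section 14.0 specifies "one dose of INI (20 International Units) or placebo".

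The product strength is also unambiguous. Section 14.1 states that Humulin R U-100 "contains human insulin (rDNA origin) 100 units/mL", and no other strength is given for this trial.

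Section 14.6 then gives the only volume for the study drug: "A volume of about 0.7 mL of insulin or placebo will be administered each time".

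On preparation, 14.4 mentions a study nurse who prepares the insulin or placebo, 14.5 says the nurse puts it into the device chamber, and 14.6 says the device releases a metered dose. None of these carries a volume, a concentration or a diluent. Section 14.2 names sterile saline as the placebo only.

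**The concern.** Dose, strength and volume are linked by one multiplication, and the three stated values do not satisfy it. Someone preparing 0.7 mL of the named product as written would load 3.5 times the intended dose.

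Three things are at stake:

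- **Interpretation.** The primary outcome is CSF insulin about 30 minutes after 20 IU. If the written volume corresponds to another dose, a positive result cannot be attributed to 20 IU from the protocol alone, nor reproduced from it. Dose may also matter for memory, a secondary outcome: in the preliminary study (3.5), delayed story recall improved at the lower insulin dose and not at the higher.
- **Safety on a literal reading.** Participants are fasted for at least 8 hours. The largest single dose that section 12.1 specifies is 60 IU once daily, and its 160 IU daily total was given as 40 IU four times a day. A literal 70 IU exceeds both single doses.
- **Verification.** The nurse who prepares the drug is an exception to the blind (14.4), so few others are placed to notice a preparation error. A pharmacist or monitor has no correct written figure to check against.

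**Working it through.** **Inputs**

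| Quantity | Value | Source |
|---|---|---|
| Intended dose | 20 IU | Synopsis, 1.1, 4.1, 5.0, 7.2, 14.0 |
| Product strength | 100 IU/mL | Synopsis (U-100), 14.1 |
| Volume administered | about 0.7 mL | 14.6 |
| Diluent, working concentration, delivered fraction | not stated | 14.0 to 14.8 |

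**Relation:** dose (IU) = concentration (IU/mL) × delivered volume (mL).

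**Step 1. Try to reproduce the 0.7 mL.** 20 IU ÷ 100 IU/mL = 0.20 mL. The stated volume is not reproduced.

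**Step 2. Dose implied by the stated volume.** 100 IU/mL × 0.7 mL = 70 IU, and 70 ÷ 20 = 3.5.

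**Step 3. Could rounding explain it?** The protocol does not say how approximate its figure is, so 0.6 to 0.8 mL is taken here as a generous assumption. 0.6 × 100 = 60 IU (3.0 times the dose) and 0.8 × 100 = 80 IU (4.0 times). It does not.

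**Step 4. Could the volume belong to the earlier trial's dose?** That trial (section 4.0) gave 40 IU daily. 40 ÷ 100 = 0.40 mL, so this does not match either.

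**Step 5. What would have to be true for 0.7 mL to carry 20 IU by dilution?** The working concentration would be 20 ÷ 0.7 = 28.6 IU/mL, made from 0.20 mL of U-100 plus 0.70 − 0.20 = 0.50 mL of diluent. Over 0.6 to 0.8 mL the concentration runs from 33.3 to 25.0 IU/mL and the diluent from 0.40 to 0.60 mL.

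**Step 6. What if 0.7 mL is an undiluted chamber load?** The device would have to release 0.20 ÷ 0.70 = 28.6% of it (33.3% to 25.0% over 0.6 to 0.8 mL).

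**Step 7. Does the text support step 5 or step 6?** No. The only insulin diluent mentioned is the placebo of the earlier multi-site trial (4.0). Saline in this trial is specified as placebo, not as something added to insulin. Section 14.6 describes the volume as administered, not loaded, and attaches no figure to the metered dose.

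**The case against.** The strongest reply is that the conflict assumes the 0.7 mL is undiluted, which the protocol never says. Sections 14.1 and the synopsis give the strength of the product as supplied, not of the solution in the device. Section 14.4 implies a preparation step, and 14.6 gives a single volume for insulin and placebo alike. Twenty IU made up to a matched 0.7 mL would satisfy every sentence. On that view the text is incomplete rather than wrong.

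Practical risk is also limited. The intended dose is not in doubt, the trial is single-site, a study nurse loads the device and directly supervises its use (14.5, 12.2), and the device is identical to the model used in two earlier studies approved by the same IRB (2.2.2). Randomization and the planned analysis are unaffected.

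Much of this stands. Dilution is a plausible benign explanation, and the 3.5-fold figure applies only to undiluted delivery. But the diluent and its quantity have to be supplied from outside the text. The safeguards lower the chance of an error without stating the missing concentration. An instruction that gives the wrong dose when followed literally with the only named product is more than a missing detail.

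The objection also raises a useful practical point: if the insulin volume is cut to 0.20 mL while saline stays at 0.7 mL, the difference could threaten participant blinding in a crossover. The correction must move both together.

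**Conclusion.** The concern holds, and the text must be corrected. For undiluted U-100, the volume in 14.6 corresponds to 70 IU against an intended 20 IU (3.5-fold; 3.0- to 4.0-fold over 0.6 to 0.8 mL), or equivalently 0.7 mL against 0.20 mL.

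This rests on the stated strength and on finding no reconciling instruction. The text between sections 12.4 and 14.0 was not available for review. Since 14.0 to 14.8 are all present, a preparation instruction there is unlikely, but that cannot be confirmed.

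The conclusion concerns the written instruction. It is not evidence that participants would be overdosed.

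**What to change.** Amend 14.5 and 14.6 so that concentration × delivered volume = 20 IU, using whichever of these describes actual practice:

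1. **Undiluted:** change the volume to 0.20 mL of Humulin R U-100 (20 IU).
2. **Diluted:** state that 0.20 mL of Humulin R U-100 is made up to 0.70 mL with a named diluent, giving about 28.6 IU/mL (20 IU in total).
3. **Chamber load:** describe 0.7 mL as the volume loaded rather than administered, and give the metered volume that delivers 20 IU (0.20 mL if undiluted).

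In every case, set out in 14.5 the preparation step that 14.4 only alludes to, and state that the saline placebo volume equals the chosen insulin volume.

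The cost is one text correction across two short sections, plus alignment of any nurse preparation worksheet. No participants, visits or procedures are added.
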